## Secondary Endpoints

- Safety and tolerability of EDP-938 compared to placebo as assessed by, but not limited to, AEs, vital signs, and clinical laboratory results;
- AUC for RSV RNA viral load measured in nasal swab samples by RT-qPCR;
- Proportion of subjects with RSV RNA viral load below the LOD in subjects receiving EDP-938 compared to placebo;
- Time to RSV RNA viral load being undetectable;
- PK parameters of EDP-938 including AUC and predose concentrations;
- Time to discharge for hospitalized subjects;
- Time to use of oxygen for hospitalized subjects who are not receiving oxygen at the time they receive the first dose of study drug;

- Proportion of hospitalized subjects requiring oxygen supplementation or have an increased oxygen requirement;
- Time to mechanical ventilation for hospitalized subjects;
- Proportion of hospitalized subjects requiring mechanical ventilation;
- Deaths among hospitalized subjects;
- Time to hospitalization for initial outpatients who are subsequently hospitalized;
- Proportion of outpatients who are subsequently hospitalized or died;
- Time to resolution of symptoms for outpatients who are not hospitalized.

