Visit	Screening	V1V	2 V.	3 V4	V5	PT1	PT2	$PT3^3$	home. (X) is for V2 and V4 assessments for hospitalized subjects.
Day	Day-1 to Day 1	1	2 (±1	()  4	5 (±1) EOT 	9 (±1)	14 (±2)	28 (±4) EOS 	Notes  ; Protocol Section
Parent/Guardian ReSVinet clinical scoring system and palatability question		Once	daily	/ from	predose D14	on D1 t	hrough		Caregiver(s) should complete the Parent/Guardian ReSVinet clinical scoring system using the eCOA handheld eDiary for both hospitalized and non-hospitalized subjects. The ReSVinet D1 assessment must be predose, and subsequent assessments should be completed predose at the same time daily ( $\pm 2$ hr) for 14 days . The palatability assessment should be completed after each dose of study drug is administered. If a caregiver is unable to use the eDiary, a paper diary may be used. Section 8.10.2
Parent/Guardian clinical scoring system)		E	wice	daily	on D1 tl	1rough I	014		Caregiver(s) should complete the Parent/Guardian clinical scoring system on paper for both hospitalized and non-hospitalized aubicets. The D1 assessment must be completed predose, and subsequent assessments should be completed twice daily, approximately every 12 hours, for 14 days. If D1 assessment is completed in the afternoon, only one assessment is expected for that day. will be will be completed in a subset of subjects. Section 8.10.3
Clinical Safety Evalus	ations								
									If Screening and V1 occur on the same calendar day, vital signs
Vital sign measurements	Х	X	X	k al	Х	Х	Х		measurements do not need to be repeated and the Screening measurements will be used as baseline values. If Screening and V1 occur on different calendar days, V1 measurements should be taken pre-dose
(including SpO 2 )									as baseline values. Starting on D1, vital signs should be performed QD on marked study site visit days. Section 8.4
Physical examination	Х		×		Х	Х	X		Full PE at Screening. Subsequent PEs done at discretion of Investigator will be targeted to new signs and symptoms, including specific assessments of changes from previous status. Section 8.6
ECG	Х				Х				12-lead ECG strongly preferred but where not possible, 6-lead ECG may be performed. If blood sampling and/or a nasal swab are scheduled for the same timepoint as ECG recording, those assessments should be done after the ECG. Section 8.5

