# 4.2 Sample Size Considerations

No formal hypothesis testing is planned for Parts 1 or 2 of this study. Therefore, no formal sample size justification is provided. Approximately 90 subjects will participate in this study: 12 subjects are planned in each cohort of the age groups in Part 1 (24 subjects in each age group). In Part 2, 20 subjects are planned in each of the age groups. Additional subjects may be added based on SSC recommendations.

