- Time to confirmed undetectable RSV RNA viral load (days) is defined as the time between the date of first dose to the first 2 consecutive post-baseline time points of

achieving RSV RNA viral load TND. Subjects with baseline RSV viral load TND will be excluded from the analysis.

Frequency counts and percentages of subjects by end of study (Day  $28 \pm 4$ ), and their respective 95% CIs will be reported using Clopper Pearson CI methods for the following endpoints summarized using the Efficacy Population.

- Proportion of hospitalized subjects requiring oxygen supplementation or have an increased oxygen requirement.
  - Subjects who are hospitalized at randomization and/or during study are included. The
    proportion will be defined by the number of subjects who develop a new requirement for
    oxygen supplementation or new increase(s) in oxygen requirements after the first dose of
    study drug, based on the response of "yes" to the "is this an increase of oxygen
    supplementation compared to previous use?" question on the Oxygen Supplementation
    CRF.
- Proportion of hospitalized subjects requiring mechanical ventilation
  - Subjects who are hospitalized at randomization and/or during study are included. The proportion will be defined by the number of subjects who developed a new requirement for mechanical ventilation after the first dose of study drug. Subjects on mechanical ventilation prior to the first dose of study drug are excluded from analysis.
- Deaths among hospitalized subjects
  - Subjects who are hospitalized at randomization and/or during study are included.
- Proportion of outpatients who are subsequently hospitalized or died
  - $\circ$  Subjects who are not hospitalized at randomization are included.
- Proportion of outpatients who died
  - Subjects who are not hospitalized at randomization are included.

The following endpoints will be summarized using the Efficacy Population. The summary statistics will include, at a minimum, the number of non-missing measurements, mean, standard deviation, median, minimum, 25th percentile, 75th percentile, and maximum.

- Time to discharge for hospitalized subjects
  - Time to first hospital discharge for subjects who are hospitalized at randomization will be defined as the time between the first dose of study drug and the first date of discharge. For subjects with continuous hospitalization, the last date of discharge from the continuous hospitalization will be used.

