  - This analysis includes subjects who are hospitalized at randomization and required mechanical ventilation at any time after the first dose of study drug. The duration of mechanical ventilation (days) is defined as the sum of each duration of mechanical ventilation (days) that occurred from the first dose of study drug to the end of study. The duration of mechanical ventilation for the initial hospitalization is calculated as date/time of the end of mechanical ventilation date/time of first dose of study drug. The duration of mechanical ventilation for subsequent rehospitalization(s) is calculated as date/time of the end of mechanical ventilation date/time of the start of mechanical ventilation. Missing start times will be imputed to 00:01. Missing end times will be imputed to 23:59.
- Time to hospitalization for initial outpatients who are subsequently hospitalized
  - Time to hospitalization for initial outpatients who are subsequently hospitalized will be calculated, defined as the time between the date/time of first dose to the first date of hospitalization.
- Time to resolution of symptoms for outpatients who are not hospitalized
  - Time to resolution of symptoms for outpatients at randomization who are not hospitalized during study, is defined as the time between the date/time of first dose to the first of 2 consecutive time points where each of the seven symptoms assessed by the Parent/Caregiver ReSVinet clinical scoring is 0 or 1. If a subject meets the resolution

definition (0 or 1 score for 2 consecutive timepoints) at baseline and Day 2, then this subject will be excluded from the analysis.

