# For time to event endpoints:

Kaplan-Meier estimates will be provided including at least median survival and its 95% CI on the combined EDP-938 and placebo for Parts 1 and 2. Kaplan-Meier plots will also be provided. Generalized Wilcoxon test will be performed to compare the EDP-938 vs Placebo. If appropriate, log-rank test will be performed as well. If required, a Cox proportional hazards model, adjusting for associated baseline assessment (if appropriate), would be considered. Subjects who did not achieve the specified event will be censored as follows:

RSV RNA viral load:

• Subjects who have not been followed through the Day 14 visit (discontinued from the study or incomplete follow-up) or completed Day 14 visit will be censored at Day 14 visit date.

Parent/Guardian ReSVinet, Professional ReSVinet, Parent/Guardian RESOLVE-P, Caregiver Global Impression of Severity (CaGI-S), Caregiver Global Impression of Change (CaGI-C):

• Subjects who have not been followed through the Day 14 visit (discontinued from the study or incomplete follow-up) or completed Day 14 questionnaire will be censored at Day 14.

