# Steroid Use:

The populations for analysis of steroid use are defined as follows:

- Subjects who received systemic corticosteroids at any time between 21 days prior to randomization and the PT 2 visit (Day 14).
- Subjects who did not receive systemic corticosteroids at any time between 21 days prior to randomization and the PT 2 visit (Day 14).

The following analyses will be analyzed descriptively for each of the above populations.

- Daily change in RSV shedding in nasal swab samples determined using RT-qPCR from baseline through the treatment phase
- AUC for RSV RNA viral load measured in nasal swab samples by quantitative reverse transcription polymerase chain reaction (RT-qPCR)
- Time to RSV RNA viral load being undetectable

Time to RSV RNA viral load being undetectable (TND) will be analyzed using two approaches as defined below:

- Time to RSV RNA viral load being undetectable (days) is defined as the time between the date of first dose to the first date during post-dose period of achieving RSV RNA viral load TND after which no further samples have detectable RSV RNA viral load. Subjects with baseline RSV viral load TND will be excluded from the analysis.
- Time to confirmed undetectable RSV RNA viral load (days) is defined as the time between the date of first dose to the first of 2 consecutive post-baseline time points of

achieving RSV RNA viral load TND. Subjects with baseline RSV viral load TND will be excluded from the analysis.

- Change from baseline of the Parent/Guardian ReSVinet total score which is defined as a sum of the score from each of the 7 parameters
- Parent/Guardian ReSVinet total score AUC will be calculated and summarized as described in *Section 4.13.2*.
- Time to resolution of RSV infection symptoms is defined as the time between the date of first dose to the first of 2 consecutive time points where each of the seven symptoms assessed by the Parent/Caregiver ReSVinet clinical scoring is 0 or 1. If a subject meets the resolution definition (0 or 1 score for 2 consecutive timepoints) at baseline and Day 2, then this subject will be excluded from the analysis.

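### Time to symptom resolution in outpatients omits every child later admitted, so the analysed set is selected on a post-randomization outcome

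*SAP*

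**What the plan says.** Protocol 2.2.2 lists, for Part 2 and the pooled population, "Time to resolution of symptoms for outpatients who are not hospitalized". SAP 3.2.2 repeats it. SAP 4.13.4 makes the condition explicit: "Time to resolution of symptoms for outpatients at randomization who are not hospitalized during study". The event is the first of two consecutive diary points at which all seven caregiver ReSVinet items score 0 or 1.

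For this group of endpoints SAP 4.13.4 states: "The summary statistics will include, at a minimum, the number of non-missing measurements", followed by mean, SD, median and quartiles. No rule assigns a value to an admitted child. SAP 4.13.5 carries the 4.13.4 secondary endpoints into the pooled data unchanged.

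Four other provisions bear on the point:

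- **Companion endpoints.** SAP 4.13.4 also reports "Proportion of outpatients who are subsequently hospitalized or died", with everyone not hospitalized at randomization in the denominator, together with outpatient deaths and time to hospitalization.
- **Diary coverage.** The Schedule of Assessments (Protocol Appendix 1) has caregivers score once daily for 14 days, "using the eCOA handheld eDiary for both hospitalized and non-hospitalized subjects".
- **An unrestricted definition.** In the steroid-use and coinfection analyses of SAP 4.13.6, "Time to resolution of RSV infection symptoms is defined as the time between the date of first dose", with no condition on admission.
- **Status of testing.** SAP 4.2 states: "No formal hypothesis testing is planned for Parts 1 or 2 of this study".

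**The concern.** Status at randomization is a legitimate way to define a subgroup. Not being admitted afterwards is an outcome. An outpatient who worsens enough to be admitted has done badly, and the plan itself counts that as a failure in a neighbouring endpoint. Here such a child leaves the analysis. If EDP-938 changes the chance of admission, the children who remain differ between arms for a reason other than randomization.

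The clause also reaches further than it needs to. It has no limit on cause and runs to the end of study at Day 28, while the diary stops at Day 14. A child whose symptoms resolved on Day 4 and who was admitted on Day 25 for something unrelated would lose a valid, observed resolution time.

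At stake is the one named secondary endpoint that asks how quickly outpatients get better, in Part 2 and in the pooled data.

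**Working it through.** **Planned numbers.** SAP 4.2 plans 12 subjects in each of 2 cohorts in 2 age groups (Part 1) and 20 in each age group (Part 2): 2 × 2 × 12 + 2 × 20 = 88, which agrees with the stated figure of about 90. With 2:1 and 4:1 allocation this gives EDP-938 4 × 8 + 2 × 16 = 64 and placebo 4 × 4 + 2 × 4 = 24. Part 1 Cohort 1 Age Group 2 is all inpatient (8 and 4 subjects). Outpatients therefore number at most 56 and 20 pooled, and 32 and 8 in Part 2. One excluded placebo child is at least 1/8 = 12.5% of the placebo outpatients in Part 2 and 1/20 = 5% pooled.

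**Illustration by hand (all inputs assumed).** In both arms 80% of outpatients resolve in 6 days and 20% in 12 days, so the true mean is 0.8 × 6 + 0.2 × 12 = 7.20 days in each arm.

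| Assumption | EDP-938 mean | Placebo mean | EDP-938 minus placebo |
|---|---|---|---|
| Placebo admits half the slow children, EDP-938 none; admitted dropped | 7.20 | (0.8 × 6 + 0.1 × 12)/0.9 = 6.67 | +0.53 |
| Arms reversed (drug raises admissions); admitted dropped | 6.67 | 7.20 | −0.53 |
| Half the slow children admitted in both arms; admitted dropped | 6.67 | 6.67 | 0, both 0.53 too short |
| 10% of placebo admitted regardless of speed; admitted dropped | 7.20 | 7.20 | 0 |
| First row, all outpatients kept, times as observed | 7.20 | 7.20 | 0 |
| First row, admitted child set to Day 14 | 7.20 | 0.8 × 6 + 0.1 × 12 + 0.1 × 14 = 7.40 | −0.20 |

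**Simulation (400,000 draws; all inputs assumed).** Times are lognormal with log-SD 0.5 and capped at Day 14. The median is 5 days in ordinary outpatients and 5, 8 or 11 days in admission-prone ones. Placebo admissions are 5% to 30%, and the drug prevents half or all of them. Except in the last bullet, it has no effect on speed.

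- Admission-prone median 8 or 11 days, admitted dropped: the drug looks slower by 0.07 to 1.48 days in mean and 0.05 to 1.15 days in median.
- One case in that range (20% admitted, half prevented, slow median 11): means 6.16 and 5.61 (+0.55), medians 5.34 and 5.00 (+0.34).
- Admission-prone median 5 days (admission unrelated to speed): difference about 0.
- Admission-prone median 8 or 11 days, admission counted as unresolved to Day 14: the drug is favoured by 0.09 to 1.66 days in mean, although it speeds no child.
- Drug shortens every time by 10%, 20% admitted, slow median 11: the true benefit of 0.56 day shows as about 0 if half the admissions are prevented, and as +0.42 day (drug slower) if all are.

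**The case against.** The plan can be read as asking two separate questions: was the child admitted, and how fast did those never admitted recover? The endpoint's name discloses the restriction, and admissions and deaths are reported with all baseline outpatients in the denominator. In the first row of the illustration, a reader would see 10% against 0% admitted beside the half-day gap. The endpoint is summarized descriptively, and SAP 4.13.5 directs inferential analysis to the viral endpoints and to symptom endpoints in Section 4.13.7. It does not name this one. All of this stands and limits the weight of the point. It does not make the resolution times comparable, because a separate admission count cannot correct a mean taken over a selected set.

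The unrestricted definition in SAP 4.13.6 also counts for something. The two steroid strata together cover the Efficacy Population, so admitted outpatients appear there, subject to the separate Day 2 exclusion. But those analyses mix inpatients with outpatients and do not repair the named endpoint. Section 4.13.7 is not in the supplied text, so an unrestricted exploratory analysis may exist.

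Two stronger readings are tempting. A reader might infer that the endpoint is biased against EDP-938. The documents do not support that: they give no admission rate, no recovery times and no link between the two, and the sign depends on what the drug does to admissions. A reader might also infer that the worst outcomes vanish from the study. They leave this endpoint but not the report, and a death at home without admission is not removed by the clause.

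**Conclusion.** The point holds as a selection problem confined to one descriptive secondary endpoint in Part 2 and the pooled population. The primary viral-load endpoint is untouched.

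A bias between arms needs two things: admission-prone children recover more slowly, and the drug changes admission. It then runs against a drug that prevents admissions and in favour of one that increases them. With equal admission rates in the illustration, the arms stay comparable but both look better than they are. The range of 0.07 to 1.48 days is conditional on assumed inputs and is not an estimate for this trial. With at most 8 placebo outpatients in Part 2 and 20 pooled, 10% admissions means 0.8 and 2 children, so sampling error will also be large.

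A reader might further infer that the exclusion serves no purpose because the diary continues in hospital. That goes too far. Item 2 of the caregiver ReSVinet scores care received (oxygen, imaging, blood sampling, respiratory support), so in-hospital scores partly reflect management. This is a reason for care in the repair, not for dropping the children.

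**What to change.** 1. Define the set as all subjects not hospitalized at randomization. Align Protocol 2.2.2, SAP 3.2.2 and SAP 4.13.4.
2. Apply the existing 0-or-1 rule at two consecutive points to diary scores as observed through Day 14, including days in hospital.
3. Use Kaplan-Meier in Part 2 as well as in the pooled data. Summaries of non-missing values would drop unresolved children again. SAP 4.13.5 already has a rule for the caregiver instruments under which subjects without the event who have not been followed through the visit or "completed Day 14 questionnaire will be censored at Day 14". Apply it here, and keep children who die before resolving as unresolved to Day 14.
4. As a sensitivity analysis, count admission before resolution as unresolved to Day 14. Label it a composite of admission and symptoms that credits prevented admissions.
5. Keep the never-hospitalized analysis as supportive.

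The cost is moderate. No new data are needed, because the diary is planned in both settings. Resolution times will be somewhat longer, and in-hospital scores will carry the item 2 effect, so the main analysis may also give some credit for avoided admissions. The wording of a named protocol endpoint must change. Protocol 11.2 requires an amendment if a principal feature is altered and allows SAP changes only before unblinding, so this has to be settled before then.

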# 4.13.5 Efficacy Analysis for Pooled Population

The primary endpoint is the daily change in RSV shedding in nasal swab samples determined using RTqPCR from baseline through the treatment phase in the pooled population (subjects from Parts 1 and 2 together).

All secondary efficacy endpoints described in *Section 4.13.4*, as well as all exploratory endpoints described in Section 4.13.7 are also the secondary and exploratory endpoints for the pooled population and will be analyzed with the pooled data from both Parts 1 and 2.

All pooled efficacy data will be summarized descriptively by EDP 938 and Placebo for each age group and combined EDP 938 and Placebo, as described in *Section 4.13.4* and *Section 4.13.7*.

Inferential statistics analysis will be performed to detect treatment effects of EDP 938 and Placebo using the Efficacy Population, mITT-3 and mITT-5 for the following RSV RNA viral endpoints as well as RSV symptom related endpoints described in *Section 4.13.7* (except for RESOLVE-P where Efficacy Population is used)

- Daily change in RSV shedding in nasal swab samples determined using RT-qPCR from baseline through treatment phase
  - Absolute change from baseline in RSV RNA viral load (outcome variable) will also be analyzed using MMRM as described below.
  - AUC for RSV RNA viral load measured in nasal swab samples by quantitative reverse transcription polymerase chain reaction (RT-qPCR) will be estimated via MMRM.
- Time to RSV RNA viral load being undetectable

Time to RSV RNA viral load being undetectable (TND) will be analyzed using two approaches as defined below:

- Time to RSV RNA viral load being undetectable (days) is defined as the time between the date of first dose to the first date during post-dose period of achieving RSV RNA viral load TND after which no further samples have detectable RSV RNA viral load. Subjects with baseline RSV viral load TND will be excluded from the analysis.
- Time to confirmed undetectable RSV RNA viral load (days) is defined as the time between the date of first dose to the first of 2 consecutive post-baseline time points of achieving RSV RNA viral load TND. Subjects with baseline RSV viral load TND will be excluded from the analysis.

Inferential statistics analysis approaches are as follows:

# For continuous endpoints with multiple timepoints:

Absolute change from baseline in the outcome of interest (outcome variable) will be analyzed using a mixed-effect model for repeated measures (MMRM) to compare EDP-938 and Placebo.

The model includes treatment group (EDP-938, placebo) and Day (all scheduled post-baseline timepoints available) as fixed effect, associated baseline (as appropriate), and treatment group-by-Day interaction term as factors. Treatment groups will be compared at scheduled post-baseline timepoints of interest. An unstructured covariance matrix will be imposed. If the unstructured covariance matrix fails to converge, then the following covariance structure will be assessed in this order: autoregressive, compound symmetry, Toeplitz. The Satterthwaite approximation will be used to estimate the denominator degrees of freedom. The least-squares means and two-sided 95% CIs of absolute change from baseline at each post-baseline timepoint will be derived via this model. The least-squares means and two-sided 95% CIs of AUC through Days 3, 5, 9 and 14 will be presented for individual groups and the difference between groups. The p-value will be presented for the difference between treatment groups at each post-baseline timepoint.

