#### 2.2 Treatment Assignment/Randomization and Blinding

The study will be double-blinded, meaning that the subjects and their caregivers, investigators, and site staff will be blinded to treatment assignment until the completion of the study.

Subjects will be randomized to a treatment group using an Interactive Web Response System.

Subjects will be randomized to the initial EDP-938 or placebo treatment group as shown below:

Part 1, Cohort 1, Age Group 1 and 2 (randomized 2:1)

- of EDP-938 orally QD for 5 days (8 subjects);
- placebo orally QD for 5 days (4 subjects).

The dose for Part 1 Cohort 2 for each age group will be determined based on review of Part 1 Cohort 1

data.

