# 4.8 Demographic and Baseline Characteristics

No statistical testing will be performed for the comparison between treatment groups on demographics and baseline characteristics. Subject demographics and baseline characteristics will be summarized descriptively using the Safety Population.

Age, Gestational Age, Body Length, Head Circumference, and Weight, RSV viral load measured by RT-qPCR (log10 copies/mL), professional and parent/guardian ReSVinet total scores, RESOLVE-P domain and composite scores, CaGI-S total score collected at baseline, and duration of RSV symptom onset (from the first sign of respiratory infection to randomization) will be summarized.

Qualitative variables such as sex, ethnicity, race, RSV type (RSV-A, RSV-B), and pathogen will be summarized using descriptive statistics. A by-subject listing will be provided.

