# 4.13 Efficacy Analyses

All efficacy analyses will be based on the Efficacy Population. Selected efficacy endpoints will also be based on the mITT-3 and mITT-5 populations. Part 1 data and Part 2 data will be summarized separately using descriptive statistics. In addition, all secondary efficacy endpoints in Part 2 as well as all exploratory endpoints will be summarized based on pooled data from both Parts 1 and 2. Inferential statistical analysis will be performed to these pooled analyses, as appropriate.

# 4.13.1 Primary Efficacy Analysis Part 1

Not applicable because the primary endpoint for this part of the study is the PK analysis (please refer to *Section 4.15.1*)

# 4.13.2 Secondary Efficacy Analysis Part 1

The following secondary endpoints will be analyzed descriptively using the Efficacy, mITT-3, mITT-5 Populations.

• AUC for RSV RNA viral load measured in nasal swab samples by quantitative reverse transcription polymerase chain reaction (RT-qPCR)

RSV RNA viral load will be measured in nasal swab samples by RT-qPCR on Days 1, 3, 5, 9 and 14. Viral load values reported as TD (Target Detected, but below LLOQ) will be set to the average of LOD (limit of detection) and LLOQ (lower limit of quantification). Viral load values reported as TND (Target Not Detected, below LOD) will be set to zero. Viral load data will be transformed using a log10 scale before analyses. In case of zero value, the log transformed value will be also set as zero. For the RT-qPCR assay used for detection and quantification of RSV A and RSV B, the LLOQ is 1000 copies/mL for RSV A and 250 copies/mL for RSV B; the LOD is 620 copies/mL for RSV A and 80 copies/mL for RSV B.

The RSV type of each subject will be decided at baseline based on the RT-qPCR test. The baseline RSV viral load result is from the nasopharyngeal swab sample taken after randomization and prior to first dose on Day 1. After the imputation of TD, TND, and log10 transformation, if the baseline RSV A viral load is greater than RSV B viral load, the baseline

RSV type is classified as RSV A. Further, if the baseline RSV B viral load is greater than RSV A viral load, the baseline RSV type is classified as RSV B.

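### The pooled MMRM gives baseline viral load one slope for Days 3, 5, 9 and 14; adding baseline-by-Day, age group and symptom duration would be a cheap improvement

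*SAP*

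**What the plan says.** For the pooled viral load endpoint, SAP 4.13.5 states: "Absolute change from baseline in the outcome of interest (outcome variable) will be analyzed using a mixed-effect model for repeated measures (MMRM". The terms are treatment, Day, "associated baseline (as appropriate), and treatment group-by-Day interaction term as factors". On the residuals it says: "An unstructured covariance matrix will be imposed". On reporting it says: "The least-squares means and two-sided 95% CIs of absolute change from baseline at each post-baseline timepoint will be derived via this model", and "The p-value will be presented for the difference between treatment groups at each post-baseline timepoint". The AUC is estimated from the same model, and the model is repeated in the mITT-3 and mITT-5 populations.

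The visits come from SAP 4.13.2: "RSV RNA viral load will be measured in nasal swab samples by RT-qPCR on Days 1, 3, 5, 9 and 14". That section also gives an undetected sample the value zero and keeps zero after the log transform. The primary window is the treatment phase, so its post-baseline swabs are those of Days 3 and 5.

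Two other baseline variables are available but are not in the model. One is age group: numbers and allocation are set within it (SAP 2.2: "Part 1, Cohort 1, Age Group 1 and 2 (randomized 2:1"). The other is time since first sign (SAP 4.8: "duration of RSV symptom onset (from the first sign of respiratory infection to randomization) will be summarized").

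**The concern.** With one baseline coefficient, the model assumes that a child who starts 1 log10 higher has the same expected difference in change at every visit. The SAP's coding makes that unlikely. A child who has cleared is scored 0, so change equals minus baseline and the slope among cleared children is exactly -1. Children still shedding follow some other slope. As the cleared share changes from visit to visit, the slope for the whole sample should move.

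The unstructured covariance describes the residuals; it does not free the slope. Where a day's slope differs from the common one, the misfit adds to that day's residual variance, and a baseline difference between arms is removed by the wrong amount. With about 24 placebo children, a chance difference in baseline is quite possible. The results affected are the day-by-day contrasts, intervals and p-values for the primary endpoint, and the model-based AUC.

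**Working it through.** **Planned size.** Part 1: 12 × 2 cohorts × 2 age groups = 48. Part 2: 20 × 2 = 40. The total is 88, which agrees with the stated figure of approximately 90. At 2:1, 12 children split 8:4; Part 2 is 16:4. EDP-938: 4 × 8 + 2 × 16 = 64. Placebo: 4 × 4 + 2 × 4 = 24.

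**Chance imbalance.** The SE of the baseline difference is SDb × √(1/64 + 1/24) = 0.239 × SDb. For an assumed baseline SD (SDb) of 1.2 to 1.5, this is 0.29 to 0.36 log10.

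**Formulas (complete data).** Let b_t be the slope of change on baseline at day t, b_c the common slope, and SDres the residual SD.
- SE ratio, common against day-specific slope: √(1 + (b_t − b_c)² × SDb² / SDres²).
- Leftover shift: (b_t − b_c) × baseline difference.

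The documents give no slopes, SDs or clearance rates, so all of these are assumptions.

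**Worked case.** Take slopes of -0.3, -0.5, -0.8 and -0.95, and residual correlation 0.5 between neighbouring visits, decaying geometrically. The GLS weights on the four slopes are then 1 : 0.5 : 0.5 : 1, and b_c = (−0.3 − 0.25 − 0.40 − 0.95)/3 = −0.63. On Day 3 with both SDs at 1.0, the SE ratio is √(1 + 0.333²) = 1.054. A one-SE imbalance leaves 0.333 × 0.239 = +0.08 log10.

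| Slopes, Days 3, 5, 9, 14 | SDb | SDres | SE inflation, % | Leftover for one-SE imbalance, log10 |
|---|---|---|---|---|
| -0.4, -0.5, -0.6, -0.7 | 1.0 | 1.0 | 1.1, 0.1, 0.1, 1.1 | +0.04, +0.01, -0.01, -0.04 |
| -0.3, -0.5, -0.8, -0.95 | 1.0 | 1.5 | 2, 0.4, 0.6, 2 | +0.08, +0.03, -0.04, -0.08 |
| same | 1.0 | 1.0 | 5, 1, 1, 5 | +0.08, +0.03, -0.04, -0.08 |
| same | 1.5 | 1.0 | 12, 2, 3, 11 | +0.12, +0.05, -0.06, -0.11 |
| -0.1, -0.2, -0.5, -0.9 | 1.5 | 1.0 | 13, 7, 0.3, 21 | +0.13, +0.09, -0.02, -0.16 |

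**Simulation, 64 v 24.** Two sets were run.
- Six scenarios with an estimated unstructured covariance and SDb 1.2 to 1.5 gave variance ratios of 1.003 to 1.232 (Day 3), 1.009 to 1.089 (Day 5) and 1.057 to 1.428 (Day 14). Square roots give SE inflation of 0 to 11%, 0.4 to 4% and 3 to 20%. The shift per 1 log10 of imbalance was +0.03 to +0.38, +0.09 to +0.26 and -0.19 to -0.63. Multiplied by 0.29 to 0.36, these become about 0.01 to 0.14 (Day 3), 0.03 to 0.09 (Day 5) and 0.05 to 0.23 (Day 14) in size.
- A separate simulation of linear log10 decline, with undetected values set to 0, gave SE ratios of 0.99 to 1.07. Mean estimates from the two models agreed within 0.004 log10.

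**Direction.** In the table, Days 3 and 5 have slopes shallower than the common one and are over-corrected; Days 9 and 14 are steeper and under-corrected. This pattern is not guaranteed. Coding to 0 drops a child at the RSV A detection limit by log10(620) = 2.79 at once, so early clearance by low-baseline children can make early slopes positive. One decay scenario gave +0.18, +0.30, +0.01 and -0.58 with b_c = 0.05. There Days 3 and 5 are under-corrected, and Day 14 is adjusted the wrong way.

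**AUC.** In the worked case, shifts per 1 log10 of 0, 0.33, 0.13, -0.17 and -0.32 at 0, 2, 4, 8 and 13 days give trapezoids of 0.33 + 0.46 − 0.08 − 1.225 = −0.515. That is −0.04 averaged over 13 days. Through Day 5 the average is 0.79/4 = +0.20, because the two early errors share a sign.

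**Other covariates.** Part 1 supplies 16/24 = 67% of placebo but 32/64 = 50% of EDP-938. Part 1 also admits onset up to 7 days, against 5 in Part 2. If age group and symptom duration explained a further 10 to 20% of residual variance (an assumption), SEs would fall by 1 − √0.90 = 5% to 1 − √0.80 = 11%.

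**The case against.** The strongest reply is that the effect is small, and on the primary days smaller still. The Day 5 loss is a few per cent, the largest figures are for Day 14 (outside the treatment phase), and one simulation found almost no loss. That stands, and it limits the rating.

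A reader might infer that the slopes must differ because nearly every child is undetectable by Day 14. The documents do not support this. They give no clearance rate by day, and Protocol 4.4.1 cites infant replication lasting beyond 30 days from onset. With slow clearance the slopes may hardly differ.

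A reader might also infer that imbalance is under-corrected throughout, or that the estimates are biased. Neither follows: the direction varies by day, and the slope misfit averages out over randomisations.

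It can be said that SAP 4.2 plans no formal testing. That statement concerns Parts 1 and 2; SAP 4.13.5 plans inference, with a p-value at each day, for the pooled primary endpoint.

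It can also be said that allocation is the same in both age groups and that mITT-3 and mITT-5 already address symptom duration. The first is true, so the gain from age group is precision only. The second restricts the sample; it does not adjust within it. Finally, the qualifier on baseline is sensible in a template that also covers instruments without a baseline, but viral load change always has one.

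**Conclusion.** The model as written has one baseline slope for four visits, and nothing in the published protocol or SAP adds a baseline-by-Day term. Given the coding of undetected values, unequal slopes are likely but not certain.

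The consequence is a modest loss of precision and a mis-correction of chance imbalance whose sign depends on the day, of the size given in the working. In the closed-form table the leftover is mostly 0.1 to 0.3 of the contrast's SE in the worked case with both SDs at 1.0, and up to about 0.7 at the extreme. It is not an invalid analysis or a systematic bias.

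The result rests on assumed slopes, SDs and decline rates, complete data, and the planned 64:24 split. The no-bias finding concerns the slope misfit alone. Whether Part 1 children actually enter later in their illness is not known from the documents. This is a cheap improvement of minor to moderate importance, held with moderate confidence.

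**What to change.** In SAP 4.13.5, add a sentence specific to viral load: the MMRM has fixed effects for treatment, Day, treatment-by-Day, baseline log10 viral load (always included), baseline-by-Day, age group, and days from first sign of respiratory infection to randomisation. Keep the general qualifier on baseline for the other endpoints. The same model then carries through to the AUC estimates, mITT-3, mITT-5 and the final-dose sensitivity analysis.

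The cost is five degrees of freedom: three for the extra slopes, one for age group and one for symptom duration, with about 88 children. The cost is relatively greater in the smaller populations. No new data are needed, since SAP 4.8 already derives symptom duration. Protocol 11.2 allows SAP changes only before unblinding, so the edit has to be made by then.
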